8.4.3 CLASSIFICATION OF AN ADVERSE EVENT

The PI or another licensed clinician who is a study member authorized on the delegation log will classify adverse events.

8.4.3.1 SEVERITY OF EVENT

The investigator should use the following definitions when assessing intensity of an adverse event:

- Mild: Infant or a biological parent has minor findings but tolerates them well, and no or minimal intervention required

- Moderate: Infant or a biological parent experiences enough symptoms or findings to require intervention
- Severe: Infant or a biological parent experiences symptoms or findings that require significant intervention

8.4.3.2 RELATIONSHIP TO STUDY INTERVENTION

All adverse events (AEs) must have their relationship to the genomic sequencing assessed. The investigator will examine and evaluate the participant based on temporal relationship and his/her clinical judgment.

The criteria below are intended as guidelines to assist the Investigator in assessing the likelihood of a relationship between the genomic sequencing testing and the adverse event. The greater the correlation with the components and their respective elements, the more likely the genomic sequencing testing caused the adverse event.

- *Exposure*: Is there evidence that the infant or biological parent had the testing performed such as: reliable history, patient records, assays run in applicable laboratories and results exist?
- *Time Course*: Did the AE follow in a reasonable temporal sequence from performance of the testing? Is the time of onset of the AE compatible with the testing being performed?
- *Likely Cause*: Is the AE not reasonably explained by another etiology such as an underlying disorder or other host or environmental factors?

The following scale of criteria may be used as a guidance (not all criteria must be present in order to be indicative of a relationship to study genomic sequencing).

Probably related to study genomic sequencing	
 • There is evidence the infant or a biological parent had the genomic testing performed • The temporal sequence of the AE onset relative to genomic testing is reasonable • The AE is more likely explained by the genomic testing than by another cause
Possibly related to study genomic sequencing	
 • There is evidence the infant or a biological parent had the genomic testing performed • The temporal sequence of the AE onset relative to genomic testing is reasonable • The AE could have been due to another equally likely cause
Unlikely related to study genomic sequencing	
 • There is evidence the infant or a biological parent had the genomic testing performed • There is no temporal relationship to genomic testing • There is another more likely cause of the AE

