8.3 SAFETY AND OTHER ASSESSMENTS

Enrolling sites must actively monitor, identify and assess adverse events (AE) in the study. Identification of AEs will be based on review of the medical record, observation by study staff and by report during the parent survey/interviews. For each AE, the investigator will determine whether the adverse event is serious, provide the duration (start and end dates), the severity grade (mild, moderate, severe), the relationship to the study testing (unlikely, possibly, and probably), action(s) taken, and the outcome. The AE assessment must be documented and retained with study files. The Investigator's signature and date on the source document that supports the causality noted on the AE form ensures that a medically qualified assessment of causality was done.

The laboratories conducting genetic sequencing for this study fall under the CLIA/CAP regulations. They continually monitor for errors and non-conforming events and will notify the study-wide PIs via phone/email of an error/event that affected a result for the infant. They will also notify the study-wide PIs if a data breach were to occur. In these instances, the study-wide PI would file an adverse event, and notify the DSMB, IRB, and NCATS as required. The laboratories are not expected to report adverse events as described in sections 8.3 and 8.4.

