8.4 ADVERSE EVENTS AND SERIOUS ADVERSE EVENTS

8.4.1 DEFINITION OF ADVERSE EVENTS (AE)

An Adverse Event for this study will only include the following:

- An untoward medical occurrence related to obtaining the study blood samples
- If findings for the infant thought to be secondary at the time results are reported are given to the research team, clinician or parent/guardian when the parent/guardian did not opt-in to receive secondary findings for their infant
- If secondary findings for a parent are reported to the research team, clinician or parent when the parent did not opt-in to receive parental secondary findings
- Intervention based on inaccurate result returned (testing error; provisional result not confirmed)
- Intervention based on wrong result returned (human error, result not accurately matched up with the correct infant)
- Untoward event related to an intervention initiated due to the genomic testing results (intervention that would not have been initiated without the genomic testing results)
- Loss of confidentiality related to study participation

- Any new untoward medical occurrence related to study participation or the genetic sequencing results
- A pre-existing condition that worsens in terms of frequency or intensity and the worsening is due to study participation/genetic sequencing results
- The infant dies due to error because the infant was enrolled in this study (erroneous result or misidentification)

Events not reported as Adverse Events for this study:

- A pre-existing condition at the time of enrollment
- A pre-existing condition that worsens in terms of frequency or intensity but the worsening is not related to study participation/genetic sequencing
- A new untoward medical occurrence that is not related to study participation/genetic sequencing results and does not result in death
- Death due to natural causes before genetic testing results are returned (i.e. prematurity)
- Death due to parent/guardian wishes to withdraw life sustaining treatment if an infant is determined to have a lethal condition by genetic testing

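### Adverse-event causality is rated only against genomic sequencing, so the relatedness label can mislead for blood-sampling harms that the protocol itself counts as adverse events

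*Combined protocol and SAP*

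**What the plan says.** Section 8.4.1 gives a closed list of ten kinds of adverse event. Among them are "An untoward medical occurrence related to obtaining the study blood samples", "Loss of confidentiality related to study participation" and "Any new untoward medical occurrence related to study participation or the genetic sequencing results". The last of these treats participation and sequencing results as two separate grounds for relatedness.

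Section 8.4.3.2 then sets the reference for causality: "All adverse events (AEs) must have their relationship to the genomic sequencing assessed". All three category labels (probably, possibly and unlikely related) refer to the study's genomic sequencing. Section 8.3 has the investigator record "the relationship to the study testing (unlikely, possibly, and probably"), and no other causality field.

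All three categories share one line, that the infant or parent actually had the testing. The evidence suggested for this includes "assays run in applicable laboratories and results exist". The unlikely category adds "There is no temporal relationship to genomic testing" and "There is another more likely cause of the AE".

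The criteria are offered as guidelines to be used with clinical judgement, and the protocol says that not every criterion has to be met.

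**The concern.** The definition admits an event because it is linked to sampling or participation. The causality rating then asks a narrower question, whether sequencing caused it. For a harm from the blood draw, the two answers can point in opposite directions: related by definition, yet unlikely related by rating.

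Blood sampling is the first risk described in Section 2.3.1, and Section 2.3.3 lists its physical harms. A relatedness column that tends to mark such harms as unlikely related would misdescribe a direct physical risk of the study's own procedures. Two sites reading the scale differently could also label identical events differently.

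**Working it through.** There is no figure to reproduce. The check sets the definition beside the scale and applies the scale to cases.

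**Step 1: sort the ten event types in Section 8.4.1 by whether a sequencing reference suits them.**

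| Event type | Number | Fit with a sequencing reference |
|---|---|---|
| Harm from obtaining the blood samples | 1 | Clear mismatch |
| Loss of confidentiality | 1 | Arguable; depends on what was disclosed and how |
| New or worsened condition due to participation or results | 2 | Mismatch when the cause is participation and not sequencing |
| Unwanted secondary findings, wrong or inaccurate results, interventions prompted by results, death from error | 6 | Fits |

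Check: 1 + 1 + 2 + 6 = 10.

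**Step 2: apply the scale to a blood-draw injury in an infant who is later sequenced.**
- Exposure: met, because the assay was eventually run.
- Time course: the injury precedes the assay, so it does not follow testing. This points to unlikely.
- Likely cause: the draw explains the injury better than the assay does. This also points to unlikely.

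Both lines that set the unlikely category apart are met on a literal reading.

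**Step 3: apply it to an infant who is sampled but never sequenced.** Section 7.2 allows withdrawal when a clinical diagnosis is reached before genomic testing is complete. Section 8.4.4 starts adverse-event collection when the consent form is signed, and the safety dataset in Section 9.3 includes every infant whose blood was taken. Such an infant can therefore have a countable sampling injury and no assay. The exposure line common to all three categories then fails, so none fits as written.

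**Step 4: apply it to a confidentiality loss.** If the cause is data handling unconnected with sequencing, the cause line points to unlikely. If sequencing data leak after testing, possibly or probably can be defended. The result is mixed.

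**Step 5: look for another causality rating that would cover sampling or participation.** Sections 8.3 to 8.4.6 contain none for adverse events. Only the unanticipated-problem definition in Section 8.5.1 asks about relatedness to participation in the research. Section 8.4.2 adds an inconsistency of its own: it excludes events related neither to participation nor to sequencing, but gives as its reason that an adverse event in this study needs a link to genetic testing. That reason is narrower than both the exclusion and the list in Section 8.4.1.

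**Step 6: check whether the rating controls reporting.** Under Section 8.4.5, non-serious events are entered within 7 business days and go to the DSMB every 6 months. Under Section 8.4.6, serious events go to the study-wide PI within 24 hours, and that PI alerts the DSMB chair within 24 hours. Neither route depends on the causality category.

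**The case against.** The best defence is that testing can be read broadly. Section 8.4.3.2 is headed as relationship to the study intervention. Its likely-cause question names the underlying disorder and host or environmental factors as rival explanations, and a draw done solely to run the test is not obviously any of these. On that reading a sampling injury could be rated probably related. The scale is also guidance, so an investigator may depart from a literal reading.

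This shows that the text is ambiguous; it does not resolve it. Section 7.1 identifies the study intervention as diagnostic tests, the exposure example points to laboratory assays, and Section 8.4.1 itself separates participation from sequencing results. Clinical judgement softens the literal outcome but leaves sites free to differ.

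A reader might go further and infer that sampling harms are hidden from the DSMB. The documents do not support that: relatedness is already the condition for recording an event, and the rating filters no report. Nor do they show that a serious sampling injury would escape capture, because the exclusion in Section 8.4.2 still names study participation.

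A conflict with the unanticipated-problem rules is not shown either. Section 8.5.1 applies its own test and does not import this rating.

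Finally, confidentiality losses should not be put on a par with blood draws. Laboratory data breaches are filed as adverse events under Section 8.3, and potential breaches are promptly reportable under Section 8.5.2, whatever the causality rating.

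**Conclusion.** The mismatch between Section 8.4.1 and Sections 8.3 and 8.4.3.2 is real and worth correcting. Its effect is a misleading or inconsistent relatedness label in the safety summaries, mainly for blood-sampling harms. It loses no events, delays no report, and touches no estimate, sample size or error rate. How many events would be mislabelled cannot be derived from the documents.

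The conclusion assumes that investigators take testing and sequencing at face value. It also assumes that the adverse-event form and its instructions, the MOP and the DSMP, which were not available, do not already direct a wider reading.

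**What to change.** In Sections 8.3 and 8.4.3.2, make the reference relationship to study participation. State that this includes blood sampling, performance of the tests, returned results or actions taken on them, and data handling. Apply the existing exposure, time-course and likely-cause questions to that reference, and reword the three category labels to match. In Section 8.4.2, reconcile the sentence that ties the adverse-event definition to genetic testing with the list in Section 8.4.1.

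A field on the adverse-event form naming the component involved would make the DSMB tables more informative, but it is optional.

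The cost is minor protocol and form wording, plus a recode of any events already entered. The documents do not say how many there are.

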8.4.3.3 EXPECTEDNESS

The investigator will be responsible for determining whether an AE is expected or unexpected. An AE will be considered unexpected if the nature, severity, or frequency of the event is not consistent with the risk information previously described for the study intervention. An AE is considered unexpected if it is not consistent with the risk information described in the protocol.

8.4.4 TIME PERIOD AND FREQUENCY FOR EVENT ASSESSMENT AND FOLLOW-UP

AEs must be actively identified from the signing of the ICF until the infant reaches one year CGA. AEs must be followed until an outcome is known. All events that cannot be resolved by 30 days after the final assessment at 1 year CGA will be considered resolved by convention and entered in the REDCap system.

8.4.5 ADVERSE EVENT REPORTING

Reporting of non-serious AEs must occur using the Adverse Event eCRF in the REDCap system according to the following:

Event	Timeframe for Site to Report	Timeframe for Study PI to Report
AE, not serious	Site enters AE into EDC within 7 business days of identification.	The study PI reports to the DSMB every 6 months and in the annual progress report to NCATS.

8.4.6 SERIOUS ADVERSE EVENT REPORTING

Reporting of SAEs must occur using the adverse event eCRF in the REDCap system according to the following:

Event	Timeframe for Site to Report	Timeframe for Study-wide PI to Report
SAE	Site reports to the study-wide PI within 24 hours of learning about the event.	The study-wide PI will alert the DSMB chair within 24 hours of learning about the event. If the SAE is also an unanticipated problem, the study-wide PI will also report to the central IRB and NCATS within 24 hours of learning about the event.

To ensure accurate clinical trial reporting and correct interpretation of safety signals, each death will be examined to determine cause. This may be difficult in the preterm infant population as there are often multiple events which contribute to death. For the

purposes of this clinical trial, the investigator will attribute the cause of death to the AE which had the greatest medical contribution to death, regardless of whether or not the event was the most proximal. For example, if an infant has a large intraventricular hemorrhage that leads to seizures and death, the death should be attributed to intraventricular hemorrhage, not seizures. The investigator should utilize all available information when attributing cause of death. Autopsy information should be utilized where available to amend the adverse event report if needed. It is recognized that the death certificate may not reflect clinical trial procedures and thus may not match the cause of death attributed by the investigator. In the rare situation for deaths in which no single AE represents the greatest medical contribution to death, the adverse event is listed as “Death not associated with an AE term” and one of the following causes must be selected: 1) death not otherwise specified (i.e. failure to thrive), 2) extreme prematurity, 3) multi-organ failure, and 4) sudden death (no documentation of cause, includes Sudden Infant Death Syndrome). For cases in which the cause of death is unclear, the final determination as to which AE or organ system the death should be attributed will be determined by the DSMB.

8.4.7 REPORTING EVENTS TO PARTICIPANTS

The parent/guardian of an infant will be told of AEs/SAEs in the course of the infant’s clinical care (i.e. untoward event related to treatment initiated from sequencing results) or in the instance of an inaccurate or wrong result returned. If the risk of participating in the study changes, re-consent of the parent/guardian or of a biological parent will occur at the discretion of the IRB and DSMB.

8.5 UNANTICIPATED PROBLEMS

8.5.1 DEFINITION OF UNANTICIPATED PROBLEMS (UP)

“Unanticipated Problems Involving Risks to Subjects or Others” (“UPIRSO”). An event is considered an UPIRSO when it meets all of the following criteria:

(1) It is unexpected (in terms of nature, severity, or frequency) given (a) the research procedures that are described in the protocol-related documents, such as the IRB-approved research protocol and informed consent document; and (b) the characteristics of the population being studied;

Unexpected events could be either medical or non-medical events.

(2) It is related or possibly related to participation in the research (i.e. there is a reasonable possibility that the incident, experience, or outcome may have been caused by the procedures involved in the research);

and,

(3) It places subjects or others [e.g. study team members or relatives of a subject] at a greater risk of harm (including physical, psychological, economic, or social harm) than was previously known or recognized

8.5.2 UNANTICIPATED PROBLEM REPORTING

Certain types of events (as defined below) and including unanticipated problems involving risks to subjects or others must be promptly reported to the IRB:

Event	Timeframe for Site to Report	Timeframe for Study PI to Report
Certain types of events (as defined below)	Sites must report the event to the study-wide co-PIs as soon as possible but no later than 8 working days after discovery or in the case of a death within 24 hours of learning about the event.	The study PI will alert the central IRB, DSMB Chair, and NIH as soon as possible after the event is discovered by the site, but in all cases within 10 working days after discovery of the event by the site. Reportable deaths, as described in this section, must be reported as soon as possible but in all cases within 72 hours after discovery by the site.

The following “certain types of events” must be promptly reported to the IRB:

A. UPIRSO (refer to definition in section 8.4.1)

B. POTENTIAL SERIOUS OR CONTINUING NON-COMPLIANCE:

Non-Compliance is defined by the Organization as the failure to follow the research protocol, federal, state, or local laws or regulations governing human subjects research, institutional policies, or the requirements or determinations of the IRB. Only incidents that may qualify as serious or continuing non-compliance must be promptly reported:

(1) Serious Non-compliance is defined by the Organization as non-compliance that either (a) significantly harms or poses an increased risk of significant harm to subjects or others, or (b) significantly compromises the rights and welfare of the subjects or the integrity of the Organization’s human research protection program.

(2) Continuing Non-compliance is defined by the Organization as a pattern of non-compliance that significantly compromises the scientific integrity of the study or the rights and welfare of the subjects or the integrity of the Organization’s human research protection program. When applying this definition, particular consideration may be given by the IRB to activity that recurs after a previous report has been evaluated by the IRB and corrective action has been instituted.

C. OTHER EVENTS THAT REQUIRE PROMPT REPORTING:

In addition to the above, investigators must also promptly report the following:

- Potential Breaches of Confidentiality: Any unauthorized disclosure of subject's personally identifiable information. Please Note: Potential breaches of confidentiality that involve protected health information (PHI) must also be reported promptly to the HIPAA Privacy Officer. Please see guidance for further detail.
- Incarceration of a parent participating in this study
- Unresolved Subject Complaints: Complaints of subjects when the complaint indicates unexpected risks or cannot be resolved by the research team.
- Other events: There may be other events that should be promptly reportable to the IRB.

Events that do not meet the above criteria should be summarized and reported to the IRB at the time of continuing review.

8.5.3 REPORTING UNANTICIPATED PROBLEMS TO PARTICIPANTS

Refer to section 8.3.7

9 STATISTICAL CONSIDERATIONS

9.1 STATISTICAL HYPOTHESES

The analysis plan is descriptive. There will be no statistical hypothesis testing.

9.2 SAMPLE SIZE DETERMINATION

The sample proportion and 95% CI for the binary outcomes of NewbornDx and rWGS will be calculated. The table below shows the 95% confidence limits of the estimated proportion for a range of proportions, assuming the sample size is 400 completed infants. For example, if the sample proportion is 0.05 for disorders detected by rWGS but not NewbornDx, the 95% CI will be 0.03 to 0.07. Since the distribution of time to diagnosis is unknown, it is difficult to speculate as to the width of the confidence interval for the mean or median. However, 40% to 60% (160 to 240 infants) are expected to have a genetic diagnosis which is a sufficient number for a precise estimate.

Table: Confidence Interval Limits with 400 infants

Proportion	Lower Limit	Upper Limit
0.05	0.03	0.07
0.10	0.07	0.13
0.20	0.16	0.24
0.30	0.25	0.35
0.40	0.35	0.45
0.50	0.45	0.55

9.3 POPULATIONS FOR ANALYSES

- ICF Dataset: All families who were approached for study participation
- Intention-to-Treat (ITT) Dataset: all consented infants
- Modified Intention-to-Treat Dataset: all consented infants for whom both NewbornDx and rWGS genomic sequencing results were returned
- Per-Protocol Dataset: all consented infants who received both NewbornDx and rWGS (modified intention-to-treat dataset) and completed the study period for the analysis of the primary and secondary objectives without clinically important protocol deviations. Clinically important protocol deviations will be identified and documented prior to the database lock.
- Time to Molecular Diagnosis Dataset: The Modified Intention-to-Treat Analysis Dataset excluding the infants who did not have a confirmed positive result
- Urgent Testing Dataset: All infants who required urgent testing per section 8.1

- Safety Analysis Dataset: All infants for whom blood specimens were obtained or data collected

